8.6.5 Adverse Event and Serious Adverse Event Reporting

The occurrence of AEs, SAEs, and Protocol Deviations (PDs) shall be reported through a unidirectional, HIPAA-compliant, web-based communication channel. Event reports may be initiated at any time by the subject or the investigator. All logging of event reports shall be retained for the duration of the study to provide proper documentation in accordance with FDA and ICH GCP requirements. The adverse event will be triaged based on subject content and urgency.

In the event of an AE, SAE, or PD, the message will be immediately sent to the Curebase team for determination of severity and relatedness to the investigational treatment. The study team will

collect information from the subject as necessary and create a final event report for logging within a specified timeframe. Reports containing AEs will be processed and documented.

Reports containing SAEs shall be completed and filed per regulatory requirements. The information in a SAE report should be completed as fully as possible and contain at a minimum:

- Subject ID number
- Start date of the event
- Description of the event
- Study physician's name
- Investigator causality assessment
- Investigator seriousness assessment

If safety information not available at the time of the first report becomes available at a later date, the study team member should submit follow-up safety information to Curebase. All SAEs should be followed up until resolution or permanent outcome of the event. The timelines and procedure for follow-up reports are the same as those for the initial report. Detailed study reporting procedures shall be standardized as documented in a formal Safety Monitoring Plan.

9 Statistical Considerations

A Statistical Analysis Plan (SAP) will be prepared and finalized before unblinding of subjects' treatment assignment. This document will provide further details regarding the definition of analysis variables and analysis methodology to address all study objectives. A blinded data review will be conducted before unblinding of subject's treatment assignment. This review will assess the accuracy and completeness of the study database, subject evaluability, and appropriateness of the planned statistical methods.

9.1 Statistical Hypotheses

The primary endpoint for this study will be the proportion of overall pain intensity responders to GDH and comparator following 12 weeks of treatment. An abdominal pain intensity responder is defined as a subject whose daily abdominal pain intensity averaged over the 4 weeks of Phase 3 (weeks 13 through 16) is 30% reduced compared to the daily abdominal pain intensity averaged over the 4 weeks of the Phase 1 run-in (weeks -4 through -1).

The proportion of responders in each treatment group in the Intent-to-Treat (ITT) population will be estimated along with corresponding two-sided 95% confidence intervals (CIs). For this study the null and alternative hypotheses that will be tested are:

- $H_0: P_1 = P_2$
- $H_1: P_1 \neq P_2$

Where P_1 and P_2 are the proportion of responders in GDH and Comparator treatment groups, respectively.

9.2 Sample Size Determination

In this study, 380 subjects will be randomized in a 1:1 ratio to GDH or comparator to ensure that at least 300 subjects complete their Week 13-16 assessment for analysis. Three hundred (300) subjects completing Phase 3 will provide at least 90% power to detect an 18 percentage point difference in response rates between the GDH and comparator treatment groups at the 5% significance level. The study was powered assuming that the comparator treatment group is expected to demonstrate a 26% response rate. To determine the expected response rate in the comparator treatment group, two studies of GDH reporting data that utilized dichotomous outcome measures were examined. The first (9) used an endpoint of % treatment responders (defined as a >50% reduction in IBS-SSS). In this study, 52% of subjects in the GDH group and 26% of subjects in the control group (usual care) were responders. A more recent study by Flik et al (12) reported an "adequate relief" response rate of 40% in the GDH group compared to 17% in the Edu control group. It is believed the response rate in the comparator treatment group in this study is likely to be ~26%.

9.3 Populations for Analyses

Enrolled Population: The enrolled population will include all subjects who sign informed consent and meet the inclusion/exclusion criteria. This population will be used for evaluation of demographics and baseline characteristics.

Intent-to-Treat (ITT) Population: The ITT population will include all subjects who are randomized to treatment. Subjects that are replaced due to failed inclusion/exclusion criteria or technical issues in the Curebase software will be excluded. This population will be used for the evaluation of efficacy and all safety analyses.

Per Protocol (PP) Population: The PP population will consist of all subjects in the ITT population with no major protocol deviations that may affect efficacy. This population will be used as a supportive analysis of the primary endpoint.

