7.2 Measures to Minimize Bias: Blinding and Randomization

7.2.1 Blinding

Blinding of participants to treatment in a psychological or behavioral intervention is generally not possible. By the nature of the intervention, subjects are aware of the type of intervention they are receiving. Instead, in studies involving a psychological or behavioral intervention, blinding the participants to the hypothesis being evaluated in the study is considered the best and most practical strategy for preventing study bias. The EASITx study incorporates this blinding strategy coupled with state-of-the-art IBS and behavioral research methodology.

The comparator-treatment platform will be identical to the GDH treatment platform, except that muscle relaxation (MR) audio recordings equal in treatment duration and frequency of

administration will be substituted for the GDH video/audio recordings. The comparator control group will listen to digital audio recordings of 7 guided muscle relaxation (MR) sessions of approximately equivalent length to the GDH sessions (see Appendix D for session scripts), as well as a daily practice session approximately equivalent in length to the GDH practice sessions (see Appendix E for script) (9). Guided MR was chosen as the comparator control treatment after consultation with the FDA because of (a) the ease with which it can be adapted to a digital format and support the creation of a comparator treatment and (b) credibility as a treatment for IBS albeit with limited demonstrated efficacy (9). The goal of this blinding strategy is to present two treatments that are credible to the study participants, who are themselves unaware of what the other study arm is, whether their assigned treatment (GDH or MR) is the one under study being compared to the other arm, or indeed whether both are active treatments being compared to each other.

The data collection (ePRO) system creates a double blind and eliminates the potential for investigator bias. metaMe staff and investigators will not have knowledge of group assignments, with the following exceptions:

- An independent statistician who will formulate the randomization tables.
- A firewalled Curebase staff member who will enter the treatment group assignment on the metaMe platform.
- A firewalled metaMe staff member (the CTO) who will monitor technical aspects of the study to ensure technical compliance to the protocol and in this capacity may have access to participant randomization assignments.

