8 STUDY INTERVENTION DISCONTINUATION AND SUBJECT DISCONTINUATION/WITHDRAWAL

8.1 Criteria for Discontinuation or Withdrawal of a Subject

GDH is a non-significant risk behavioral intervention. Given this, there are no foreseeable safety-related reasons to discontinue the study. Subjects may freely withdraw their individual participation in the study at any time. However, in case there is a reason for discontinuation or withdrawal of the subject from the study this should be recorded in the eCRF using the following categories (for screen failure subjects, refer to [Section 5.4](#)):

1. Treatment discontinuation due to an AE. The subject has experienced an AE that in the opinion of the investigator may expose them to undue risk or could interfere with his/her continued participation in the study.
2. Important protocol deviation. The discovery post randomization that the subject failed to meet protocol entry criteria or did not adhere to protocol requirements, and continued participation poses an unacceptable risk to the subject's health, following consultation with the sponsor or designee.
3. Lost to follow-up. The subject stops responding to requests and reminders for data collection or treatment and attempts to contact the subject were unsuccessful. Attempts to contact the subject must be documented in the subject's electronic source documents.
4. Voluntary withdrawal. The subject (or subject's legally acceptable representative) wishes to withdraw from the study. The reason for withdrawal, if provided, must be recorded in the eCRF. Note: All attempts should be made to determine the underlying reason for the withdrawal and where possible, the primary underlying reason should be recorded (i.e., withdrawal due to an AE should not be recorded in the "voluntary withdrawal" category. Similarly, lack of efficacy should not be recorded in the "voluntary withdrawal" category).
5. Study termination. The sponsor, IRB, or regulatory agency terminates the study.
6. Subject is found to have a life-threatening medical illness or serious mental health disorder
7. Any other clinical event or finding that, in the opinion of the study team, jeopardizes subject safety, privacy, or the scientific validity of the study.

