8.2 Procedures for Discontinuation or Withdrawal of a Subject

The investigator may discontinue a subject's study participation at any time during the study when the subject meets the study termination criteria described in [Section 8.1](#). In addition, a subject may discontinue his or her participation without giving a reason at any time during the study. Should a subject's participation be discontinued, the primary criterion for termination must be recorded by the investigator. Subjects withdrawn by the sponsor due to investigator error in applying protocol inclusion/exclusion criteria or technical issues in the Curebase software that

prevent appropriate execution of the trial will be replaced. Otherwise, subjects will not be replaced.

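### The set labelled ITT drops randomised subjects whom the sponsor withdraws and replaces, with no time limit or stated blinding condition, and serves efficacy and all safety analyses

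*Combined protocol and SAP*

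**What the plan says.** Section 9.3 (Populations for Analyses) starts the ITT population from all randomised subjects and then removes some of them: "Subjects that are replaced due to failed inclusion/exclusion criteria or technical issues in the Curebase software will be excluded". Of the resulting set it says: "This population will be used for the evaluation of efficacy and all safety analyses". No separate safety population is defined.

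The other two populations do not bring back a subject replaced for an eligibility failure. For PP: "The PP population will consist of all subjects in the ITT population with no major protocol deviations that may affect efficacy". For Enrolled: "The enrolled population will include all subjects who sign informed consent and meet the inclusion/exclusion criteria".

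Section 8.2 says who is replaced: "Subjects withdrawn by the sponsor due to investigator error in applying protocol inclusion/exclusion criteria or technical issues in the Curebase software". For the second cause, the fault must be serious enough to stop the trial from being run properly. It allows no other replacement. It gives no cut-off such as the first session, no cap, and no condition on what the decision-maker may have seen.

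Section 8.1 recognises late detection of entry failures: "The discovery post randomization that the subject failed to meet protocol entry criteria or did not adhere to protocol requirements". That category also requires an unacceptable risk to the subject's health.

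On blinding, Section 7.2.1 states: "metaMe staff and investigators will not have knowledge of group assignments, with the following exceptions". The exceptions are the independent statistician, a firewalled Curebase staff member, and a firewalled sponsor staff member who monitors technical aspects.

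Section 9.4.1 keeps the available data of premature withdrawals (before the end of Phase 3) in all analyses, lists all collected data, and summarises withdrawals with their reasons. Section 9 plans a blinded data review that covers evaluability, but does not say that it governs replacement.

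**The concern.** An intention-to-treat set protects the comparison because nothing that happens after assignment can change its membership. Here membership depends on a sponsor decision that can come after assignment. Eligibility errors may be found late, and faults in the Curebase platform, which collects the daily pain score, can occur at any time up to the end of follow-up. On the wording of Section 9.3, a subject replaced after Phase 3 would lose an outcome already observed.

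Two things are at stake in a pivotal trial. The primary comparison could be exposed to selection, and a reader who takes ITT at its usual meaning would be misled about who was analysed. The between-arm adverse event comparison, which Section 4.2.2 makes the safety evaluation, would also omit people who received treatment.

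**Working it through.** **1. The plan's own figure.** Inputs from Section 9.2: 300 completers (150 per arm), 26% v 44%, two-sided 5%.

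- Mean proportion 0.35; null SE = √(2 × 0.35 × 0.65 / 150) = 0.0551.
- Alternative SE = √((0.26 × 0.74 + 0.44 × 0.56) / 150) = 0.0541.
- Power = Φ((0.18 − 1.96 × 0.0551) / 0.0541) = Φ(1.33) = 90.9%. Exact binomial enumeration gives 90.7%.
- Recruitment: 300 / 0.80 = 375, so 380 is enough.

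The stated power of at least 90% is reproduced, and this point does not dispute it.

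**2. False-positive rate under removal.** Method: exact binomial enumeration with 26% response in both arms. Success follows Section 9.4.2: significant, and a difference of at least 10 percentage points. A pooled z test (z > 1.96, favouring GDH) stands in for the stratified Cochran-Mantel-Haenszel test. All removals are of non-responders, and all removal counts are assumed.

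| Removal | 150 per arm | 190 per arm |
|---|---|---|
| None | 2.48% | 1.52% |
| Equal, 5 per arm | 2.56% | 1.52% |
| Equal, 10 per arm | 2.69% | 2.03% |
| Blind to arm, 10 in total | 2.44% | 1.48% |
| Blind to arm, 20 in total | 2.50% | 1.72% |
| Blind to arm, 38 in total | 2.52% | 2.05% |
| GDH only, 5 | 3.72% | 2.03% |
| GDH only, 10 | 5.24% | 3.36% |
| GDH only, 19 | not used | 6.86% |

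The blind rows split the removals between arms at random (hypergeometric). Without the 10-point condition the blind rows stay between 2.50% and 2.53%. The drift at 190 per arm is therefore mostly a whole-number effect of that condition: 0.10 × 190 needs 19 extra responders, while 0.10 × 180 needs 18.

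**3. How few removals could move one result.** Take 67/190 v 49/190. The difference is 35.3% − 25.8% = 9.5 points with p = 0.045, so the 10-point condition fails. Remove four GDH non-responders: 67/186 v 49/190 is 36.0% − 25.8% = 10.2 points with p = 0.032, and both conditions are met. This is a constructed example that needs removal from one arm only.

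**4. Adverse event summaries.** If k of 190 treated subjects in an arm are replaced for reasons unrelated to adverse events, a given subject's event leaves that arm's summary with probability k/190: 5/190 = 2.6%, 10/190 = 5.3%, 19/190 = 10%. With event probability q, the expected percentage is (190 − k)q / (190 − k) = q, which is unchanged. Counts and some precision are lost. The expected percentage shifts only if replacement is related to adverse events.

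**5. Section 9.4.1 beside Section 9.3.** One keeps the data of premature withdrawals in all analyses; the other removes replaced subjects from the set. They agree only if all analyses means all analyses within each population, which the text does not say. For the at-assessment primary analysis the overlap is small: a withdrawal before the end of Phase 3 with at least 0.50 × 28 = 14 Phase 3 days recorded. Multiple imputation and the repeated-measures models are also affected. After Phase 3 the Section 9.4.1 sentence no longer applies.

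**The case against.** The strongest reply is that the protocol states this modified set openly and little harm follows. Much of that stands.

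- **The grounds are narrow.** Eligibility is fixed by facts that precede assignment, and the Curebase platform collects data in the same way in both arms.
- **The blind is real.** Sponsor staff and investigators do not know assignments, and no section gives the firewalled exceptions a part in replacement. A reader might infer that the exclusion inflates the type I error or favours GDH. The documents do not support that: arm-blind removal is negligible even when it targets non-responders.
- **Adverse events do not vanish.** A reader might infer that safety data are lost or that event rates are biased. The events are still recorded and listed, and expected percentages hold if replacement is unrelated to them.
- **Withdrawals and reasons are already to be summarised.** Only an explicit split by arm is missing.
- **Sections 9.3 and 9.4.1 need not contradict each other.** Reading the latter within each population is natural, so this is a tension to resolve.
- **A separate SAP is referred to and its text is not in the document.** It may add a timing or blinding condition, so the finding is limited to the text available.

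The reply does not make the label accurate. Nothing in the text ties the replacement decision to the blind or to a date, and no defined population keeps a treated subject who was replaced for an eligibility error.

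**Conclusion.** The concern holds as a defect of definition that should be fixed. Followed as written, the plan deletes randomised subjects from a set called ITT, at a time and on information that it does not restrict. The consequence for efficacy is an exposure to selection; no bias is demonstrated. Under the assumed counts, arm-blind removal leaves the one-sided error at about 2.5% (150 per arm) or 1.5% to about 2% (190 per arm). It becomes material only if removal follows both arm and outcome, as with 10 GDH non-responders: 5.2% or 3.4%. For safety, by-arm summaries lose the events of treated but replaced subjects, with no expected change in percentages unless replacement is related to those events.

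Confidence is high on the wording. The sizes are illustrative: they rest on assumed removal counts, a 26% response rate in both arms, and an unstratified test.

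**What to change.** 1. In Section 9.3, define ITT as all randomised subjects analysed as assigned, with missing Phase 3 data handled by the methods already planned.
2. Move the replacement exclusions to the PP population or to a sensitivity analysis, with membership decided at the blinded data review.
3. Base adverse event summaries on all randomised subjects. A set of subjects who started a session may be added as a supplement, but should not be the only one: Section 2.3 allows up to 7 days between randomisation and treatment start, and events in that gap would drop out.
4. Add a by-arm split to the withdrawal summary planned in Section 9.4.1.
5. State in Section 9.4.1 whether all analyses means within each population, and reconcile it with Section 9.3.

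Replacement may continue; the originals simply stay in the set.

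**Cost.** Wording only, plus possible dilution. Replaced subjects without usable Phase 3 data stay missing in the at-assessment analysis, so power there is unchanged. If they contribute outcomes at an assumed 26% in both arms, added to 150 completers per arm at 44% v 26%, exact power falls from 90.7% to 90.1% (5 per arm), 89.4% (10) or 87.9% (19). The last two are below the planned 90%, a modest price that arises only if replacements are that frequent.

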9.4 Statistical Analyses

9.4.1 General Approach

The SAS System, Version 9.4 (or higher), will be used for all analyses, unless otherwise specified. Continuous variables (e.g., age) will be summarized using the number of observations (n), mean, standard deviation (SD), median, minimum, and maximum. Categorical variables (e.g., sex, race) will be summarized using the number of observations (n) and percentage in each category.

All data used in analyses and/or collected during the study will be provided in listings. Subjects withdrawn prior to end of Phase 3 (Weeks 13-16) assessment period will be considered as prematurely withdrawn. All available data for subjects who prematurely withdraw from the study will be included in all analyses. All 4-week assessment periods in MMRM and GEE models will include: Phase 1 (weeks minus 4 through minus 1), Phase 2 weeks 1-4, Phase 2 weeks 5-8, Phase 2 weeks 9-12, Phase 3 (weeks 13-16), LTE Period 1 (weeks 35 through 38), and LTE period 2 (weeks 61 through 64). At timepoints during the study that require 4 weeks of daily IBS symptom and pain assessment, at least 50% of the required assessments must be collected to be able to derive the average daily abdominal pain intensity and like endpoints. Study withdrawals, reasons for withdrawal, and missing assessment collections will be summarized.

Analyses of treatment will be performed using two different approaches to account for missing data during the treatment phase:

1. At-assessment Analysis: Missing values at post-baseline assessments will not be replaced and will be regarded as missing in analyses.
2. Multiple Imputation: Missing values at post-baseline assessments will be imputed using the multiple imputation method.

Additional details of the statistical methods are provided in the SAP.

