6.5 Strategies for Recruitment and Retention

The study seeks to enroll adult subjects, ages 18 to 70 years of age, who have a confirmed diagnosis of IBS via the Rome IV diagnostic criteria. To meet the enrollment goal of approximately 380 randomized subjects and 300 evaluable subjects (estimated maximum 20% study dropout rate) patients will be recruited from participating clinic populations (study physicians will be authorized to screen their own subject population for eligibility) and subjects who have been recruited and prescreened via online, digital channels.

Planned traditional recruitment channels include:

- Distribution of flyers to our clinics
- Distribution of flyers to university health centers
- Informational outbound phone calls to subjects from study staff
- Referrals by family members of subjects to the study

Planned digital recruitment channels include:

- Social media community groups
- Facebook
- Craigslist
- Instagram

It is desirable to enroll many minorities and women and create a diverse population. 60-65% of IBS subjects are female. No special action will be employed to ensure adequate female enrollment.

Subjects will be compensated for participation in the study.

Participants will receive their compensation payments via Curebase so long as they continue to contribute data consistently. Payments will be withheld for subjects that fail to complete ≥ 5 out of 7 of the weekly abdominal pain score surveys. Participants will be provided a warning after they miss 1 of the weekly data collection points.

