9.4.2 Analysis of the Primary Efficacy Endpoint(s)

The primary endpoint, proportion of overall pain intensity responders is defined as a subject whose daily abdominal pain intensity averaged over the 4 weeks of Phase 3 (weeks 13 through 16) is 30% reduced compared to the daily abdominal pain intensity averaged over the 4 weeks of Phase 1 (weeks -4 through -1) (27). Responders will be compared between the GDH and comparator treatment groups using a Cochran-Mantel-Haenszel test adjusted for IBS subtype and gender. If the resulting p-value is less than 0.05 and the magnitude of the difference in pooled proportions is at least 10 percentage points, then it will be concluded that the primary endpoint has been met.

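### Two unranked missing-data analyses sit behind one success rule; the text does not say which decides, and the at-assessment one is not the ITT estimate

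*Combined protocol and SAP*

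**What the plan says.** Section 9.4.1 states "Analyses of treatment will be performed using two different approaches to account for missing data during the treatment phase". The first approach is at-assessment: "Missing values at post-baseline assessments will not be replaced and will be regarded as missing in analyses". The second is multiple imputation of missing post-baseline values. The imputation model, its variables and its missingness assumption are not given. A four-week average needs at least half of its daily entries.

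Section 9.4.2 compares responders with one Cochran-Mantel-Haenszel (CMH) test and states one rule. It begins "If the resulting p-value is less than 0.05" and adds a minimum difference of 10 percentage points. It does not say which handling of missing data produces that p-value or that difference.

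On the population, Section 9.1 says "The proportion of responders in each treatment group in the Intent-to-Treat (ITT) population will be estimated". Section 9.3 defines ITT as all randomised subjects apart from those replaced, and names only the Per Protocol analysis as supportive.

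On numbers, Section 9.2 says "380 subjects will be randomized in a 1:1 ratio to GDH or comparator" and gives the purpose as "to ensure that at least 300 subjects complete their Week 13-16 assessment for analysis". Section 6.5 puts attrition at "estimated maximum 20% study dropout rate".

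**The concern.** Two analyses give two p-values and two differences, while the rule expects one of each. The 10-point condition is a hard cut-off, so a change of denominator from completers to all randomised subjects can reverse the verdict without any change in the observed data.

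The two approaches are also not equivalent. At-assessment compares only subjects with enough Phase 3 diary data. If subjects who are not improving leave GDH more readily than the comparator, the remaining GDH group looks better than the randomised group. Such dropout is foreseeable: Section 8.1 asks that withdrawal for lack of efficacy be recorded separately from voluntary withdrawal. MI can use the diary entries made before a subject left, but the text does not commit it to do so.

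The scope is unclear as well. The lead-in limits both approaches to the treatment phase, which Section 5.1 defines as weeks 1-12, while the primary endpoint lies in weeks 13-16. The list items speak of post-baseline assessments, which would include Phase 3. Read literally, the lead-in leaves the primary endpoint with no stated method.

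**Working it through.** **1. The plan's own power.** Section 9.2 says 300 completers "will provide at least 90% power to detect an 18 percentage point difference in response rates". Inputs: 150 per arm, comparator 26%, GDH 26 + 18 = 44%, two-sided 5%. With pooled rate 0.35, the null standard error is √(2 × 0.35 × 0.65 / 150) = 0.0551. The alternative standard error is √((0.44 × 0.56 + 0.26 × 0.74) / 150) = 0.0541. Power = Φ((0.18 − 1.96 × 0.0551) / 0.0541) = Φ(1.33) = 90.9%. The figure reproduces, and it is a completer figure.

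**2. How many may lack a Phase 3 result.** 380 − 300 = 80, and 80 / 380 = 21.1%, or 40 per arm if split equally.

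**3. How the two planned analyses can part.** Take 57/150 responders on GDH and 39/150 on the comparator (illustrative counts, single-stratum CMH).
- At-assessment: 38.0% − 26.0% = 12.0 points. The pooled rate is 96/300 = 0.32, the standard error √(0.32 × 0.68 × 2/150 × 300/299) = 0.0540, z = 2.22 and p = 0.026. Rule met.
- Imputed over 190 per arm: the difference is (57 − 39 + k) / 190, where k is the average net number of extra GDH responders imputed among the 40 missing in each arm. Ten points need 19 net responders, so k must be at least 1. The imputed rates must therefore favour GDH by at least 1/40 = 2.5 points. If the missing subjects in both arms are imputed at the same rate, k = 0 and the difference is 18/190 = 9.5 points. Rule not met.

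**4. How often it happens.** The documents give no joint distribution of Phase 2 and Phase 3 pain, so this step rests on assumptions: 190 per arm, comparator rate 26%, correlation 0.7 between weeks 9-12 and Phase 3, about 21% missing, no strata, 2,000 trials per setting, MI using weeks 9-12 pain, and success counted only in favour of GDH. Where dropout is informative, it is so in GDH only.

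| Dropout | True difference (points) | At-assessment succeeds | MI succeeds | Verdicts differ |
|---|---|---|---|---|
| Unrelated to outcome | 0 | 2.2% | 1.3% | 1.3% |
| | 12 | 61.5% | 62.8% | 9.7% |
| | 18 | 90.8% | 92.9% | 3.9% |
| Higher in GDH subjects doing poorly at weeks 9-12 | 0 | 11.8% | 1.4% | 10.4% |
| | 12 | 88.5% | 63.6% | 24.9% |
| | 18 | 99.1% | 94.0% | 5.1% |
| Higher in GDH subjects with poor unseen Phase 3 outcome | 0 | 18.5% | 5.5% | 13.0% |
| Same, 26% missing in GDH and 16% in comparator | 0 | 27.2% | 7.9% | 19.3% |

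In the second block at-assessment estimates on average 4.1, 17.2 and 23.5 points where the truth is 0, 12 and 18. MI estimates −0.1, 12.0 and 18.0. A second simulation under other assumed settings put disagreement with differential dropout as high as 29% near 12 points, disagreement near 18 points as high as 7%, and null success at about 22% for at-assessment against 2% for MI.

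**5. Dropout on unseen outcomes.** The last two rows show that MI from the diary reduces this bias without removing it. The text contains no delta adjustment, reference-based imputation, tipping-point analysis or non-responder rule.

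**The case against.** The strongest reply is that the details are deferred. The opening of Section 9 says the SAP will be final before unblinding and that a blinded data review will consider evaluability and methods. Section 8.3 sends subjects with too few Phase 3 surveys to the SAP for classification, and Section 9.4.1 also refers to it. The separate SAP text is not in the material reviewed, so it may already settle the matter. This limits the point to what the supplied text leaves open. It does not remove it, because Section 9.4.1 already commits to both analyses and Section 9.4.2 states the rule without a tie-break.

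Three stronger readings are tempting, and the documents do not support them.
- A reader might infer that the sponsor can choose the verdict after unblinding. The SAP timing in Section 9 speaks against that. Nor is the mere choice costly in every setting: in one null simulation (4,000 trials, dropout modelled on the weeks 9-12 change, CMH over six strata where Section 7.2.2 has eight), at-assessment succeeded in 5.0%, MI in 2.8% and either in 5.4%. The choice added 0.4 points over at-assessment alone.
- A reader might infer that neither method can deal with subjects who leave for want of relief. MI can, where the lack of relief was recorded in the diary before they left. The gap is dropout driven by outcomes nobody recorded.
- A reader might infer that MI must be less favourable to GDH. In the same six-strata work MI succeeded more often than at-assessment: 36.4% against 32.9% at 8 points, and 73.4% against 63.9% at 13 points.

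It is also fair to say that the risk is concentrated near the 10-point threshold, and that 20% dropout is the plan's stated maximum.

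**Conclusion.** The point stands in this form: in the supplied text the deciding analysis for the primary success rule is not named, its application to weeks 13-16 is unclear, and one of the two candidates is a completer analysis that does not match the ITT estimate. At-assessment is open to bias when poor responders leave one arm more often, and nothing planned examines dropout that depends on unseen outcomes.

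The size is moderate. Verdicts differ in about 10% of trials near a true 12-point effect (25-29% with differential dropout in GDH) and in about 4-7% at the planned 18 points. With that dropout and no true effect, at-assessment succeeds in about 12-22% of trials, against 1-2% for MI using Phase 2 diary data. These rates depend on the assumed correlation, dropout mechanism and imputation model, and on about 21% missing, so they show order of size only. The gaps in the text and the arithmetic in steps 1 to 3 do not depend on the simulations. This should be fixed, but it does not invalidate the design.

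**What to change.** Before unblinding, amend Sections 9.4.1 and 9.4.2, or the SAP, as follows.
- Name MI on the ITT population as the one deciding analysis for the weeks 13-16 responder endpoint, and reword the lead-in so that it covers Phase 3.
- Impute the continuous Phase 3 average pain from the Phase 1 average, the Phase 2 period averages, arm, gender and IBS subtype, then derive response in each imputed data set.
- Combine the CMH statistic and the difference in proportions across imputations, and apply both success conditions to the combined result.
- Label at-assessment as a sensitivity analysis.
- Add one delta (tipping-point) analysis that reports how much worse the missing GDH subjects would have to be for either success condition to fail. Non-responder imputation is optional.

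No new data are needed, since Table 1 already has daily pain in Phases 1 to 3. The cost is SAP wording and a few extra programs. The sponsor gives up the choice between two results, and the estimate may move in either direction.
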